##### **1.3.1.2. Plasma Pharmacokinetics of PF-06741086 Following Administration of Single IV and SC Doses of PF-06741086**

A summary of PK parameters following single dose SC administration of PF-06741086 at 30, 100, and 300 mg and single dose IV infusion over 1 hour at 150 and 440 mg is presented in [Table 3](#).

Peak plasma concentration ( $C_{max}$ ) was reached at 1 hour, ie, first sample collection at the end of infusion, following IV administration and 48 to 108 h following SC administration. Under the same dosing route, exposures (particularly AUC) appeared to increase greater than proportionally with dose, which suggests that PF-06741086 may undergo target-mediated drug disposition. As dose increases, mean terminal half-life of PF-06741086 increased from 33.3 h (100 mg SC) to 79.5 h (440 mg IV) in non-Japanese subjects.

**Table 3. Descriptive Summary of Plasma PF-06741086 Pharmacokinetic Parameters Following Single SC and IV Doses, Study B7841001**

Parameter (units)	Parameter Summary Statistics by PF-06741086 Treatment Group					
	30 mg SC	100 mg SC	300 mg SC	300 mg SC Japanese	150 mg IV	440 mg IV
N, n	4, 0	6, 4	6, 3	4, 2 b	6, 6	6, 5
AUC inf (ng.hr/mL)	NC	257700 (34)	2799000 (83)	4955000 (4240000-5670000)	2608000 (16)	14380000 (19)
AUC last (ng.hr/mL)	0	81890 (391)	3120000 (68)	3551000 (28)	2346000 (14)	14290000 (21)
C max (ng/mL)	0	1183 (287)	16490 (63)	18500 (25)	45640 (5)	152800 (12)
T max (hr)	NR	48.0 (48.0-72.0)	72.0 (48.0-144)	108 (72.0-144)	1.07 (1.05-2.00)	1.54 (1.08-2.00)
t ½ (hr)	NC	33.30 ± 5.39	65.77 ± 18.00	98.35 (74.7-122)	43.58 ± 4.95	79.46 ± 17.71

N = Number of subjects contributing to the summary statistics; n = number of subjects for t½ and AUCinf.

NC=Not Calculated.

NR = Not reported: summary statistics are not presented for n<3.

a Geometric mean (geometric %CV) for all except: median (range) for Tmax; arithmetic mean ±SD for t½.

b Median and range presented since N=2.

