### **1.3.3. Dose Rationale**

#### **1.3.3.1. Starting Dose**

The starting dose for this study is 300 mg PF-06741086 SC once weekly (QW). The safety, PK, and PD results from study B7841001 ([Section 1.3.1](#)) were used to establish the starting dose in this study.

All dose levels (30-300 mg for SC, 150 and 440 mg for IV) evaluated in study B7841001 were safe and well-tolerated in healthy adult subjects; as such, the maximum tolerated dose (MTD) was not identified. In addition, as the primary target organ for pharmacologic effect of PF-06741086 in non-clinical toxicity studies was the coagulation cascade, the MTD in subjects with hemophilia would likely be higher than the MTD in healthy subjects with intact coagulation systems.

The efficacious dose of PF-06741086 was defined to have a trough concentration in the range of that conferring approximately 90% to 99% of maximum effect in the PD biomarker assay (EC90 to EC99). This was selected as an approximately similar range indicated modulation of the in vivo biomarkers of PF1+2 and D-dimer reported with concizumab (a different anti-TFPI antibody) in healthy subjects and subjects with hemophilia. Based on data from study B7841001, population PK/PD analyses of PD biomarker (ie, dPT, TGA peak thrombin, and PF1+2) data was conducted using nonlinear mixed-effects modeling with NONMEM (version 7.3). EC90 estimated from the peak thrombin, dPT and PF1+2 models

were 0.765, 2.84, and 35.4 µg/mL, respectively. While the EC90 of dPT is similar to that derived from a study in normal cynomolgus monkeys, ie, 2.25 µg/mL, the upper end of the wide range of EC90 derived from the three biomarkers (dPT, peak thrombin, and PF1+2) from B7841001 was also considered when the starting dose was selected to maximize the chance of achieving efficacy in hemophilia A and hemophilia B subjects. The predicted Ctrough,ss is 67.3 µg/mL following 300 mg weekly SC dosing of PF-06741086.

At the starting dose of 300 mg weekly SC in the current study, the steady state (SS) exposures (Cmax and AUC168) are predicted to be more than 150-fold lower than the PK stopping limits (Section 3.3). The predicted steady state (SS) exposures (Cmax and AUC168) at the starting dose are also lower than what were observed following single doses of 440 mg IV, the highest dose level evaluated in study B7841001.

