### 1.3.3.2. Dose Progression

The dose progression in the study will be guided by observed safety, PK (including predicted exposures at subsequent dose levels), PD and/or efficacy. Regimens between the starting and highest doses will be selected with the intent to bracket the expected clinically efficacious exposure range in humans and to provide safety coverage for the expected clinically relevant dose range. PF-06741086 dose levels and/or regimen(s) may be modified after the first dose such that they can be administered at a higher or lower dose, by a different route (SC or IV), frequency (weekly or monthly), and with or without a loading dose, based on emerging data. However, they will not exceed the PK exposure or dose limitations for dose escalation (Section 3.3). The highest dose for SC dosing will also be determined by the total number of injections that can be safely administered in hemophilia patients.

Table 4 illustrates current predictions of the human PK based on data from Study B7841001 and the safety margins for the planned dose progression scheme. Nominal PF-06741086 doses planned are 300 mg SC QW, 150 mg SC QW (with a 300 mg SC loading dose), 450 mg SC QW, and 1000 mg IV QM.

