### **3.2. Study Duration**

Subjects will be screened within 35 days prior to administration of the investigational product to confirm that they meet the subject eligibility criteria for the study. At the Day 1 clinic visit, eligibility criteria will be confirmed. Subjects will begin dosing on Day 1. Subjects will be required to return to the clinic (eg, study site) for PK/PD sample collection on Day 2 and Day 4. Subjects will then be required to attend weekly clinic visits on Day 8, Day 15, Day 22, and Day 29. For subjects with once weekly (QW) dosing frequency, investigational product will be administered at these visits as well.

Following Day 29, provided that safety was confirmed for the cohort and no stopping criteria were met, all subjects in each cohort will return to the clinic for PK/PD sample collection on Day 30 and Day 33. Subjects in the SC cohorts will receive treatment on Day 36, Day 43, Day 50, Day 57, Day 64, Day 71, Day 78, follow-up on Day 85, and end-of-study procedures on Day 113. For the Day 36, 43, 50, 64, 71 and 78 SC treatments, in countries where approved by respective competent authorities and at sites where it is approved by the respective IRB/EC, SC treatment with investigational product may be administered by investigator site personnel in a home care or ambulatory clinic setting. Subjects in the IV cohort will receive treatment on Day 57, follow-up on Day 85, and end-of-study procedures on Day 113.

Subjects with positive ADA or NAb results may be requested to return for additional follow-up visits after Day 113.

Subjects who experience a treatment-related adverse event (including lab abnormalities) at any time point will continue to be followed through resolution or stabilization of the event as agreed upon by the investigator and Sponsor.

The maximum total duration of the study for a single subject, from initial screening to final follow-up, will be approximately 5 months.

During the study data will be reviewed on an ongoing basis to determine if PF-06741086 is safe and tolerated. Dosing of subjects in any cohort may be stopped if the B7841002 protocol-specified stopping criteria are met ([Section 3.3](#)). If available data are permissive for dose progression, subjects will be recruited into the next cohort in the study and dosed at the next dose level of PF-06741086.

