- If, based on the observed data, the group geometric mean  $C_{\max}$  or area under the curve ( $AUC_{168}$ ) (based on total concentration with either the first dose or at steady-state) of the next planned regimen is projected to exceed the exposure limits ( $AUC_{168}$  of 1,940,000  $\mu\text{g}\cdot\text{h}/\text{mL}$  and  $C_{\max}$  of 27,800  $\mu\text{g}/\text{mL}$ ), that dose will not be explored. Modified doses may be explored if they are not expected to exceed these PK stopping criteria.

In addition, tolerability criteria for dose escalation are:

- For SC cohorts: no more than 2 subjects in a dosing cohort of 6 subjects experience at least moderate severity injection site reactions.
- For IV cohorts: no more than 2 subjects in a dosing cohort of 6 subjects experience at least moderate severity infusion/injection site reactions.

Progression to a higher dose level or regimen not assessed as safe and well tolerated in a previous cohort will follow the Sponsor's review of the available safety, PK, PD, and bleed rate data through study Day 29 (at a minimum) in 100% (ie, 6 of 6) of subjects in the current cohort. Accumulated safety, PK, PD, bleed rate and immunogenicity data from previous cohorts will also be reviewed. Progression to the next cohort will occur if the current dose level is well tolerated and after satisfactory review of these data.

For doses with projected  $C_{max}$ /AUC levels not previously achieved in humans, sequential dosing will be implemented for the first 3 subjects at the respective dose level. Following initial dosing for each of the first 3 subjects, available safety and laboratory data through 72 hours post-dose will be monitored. Subsequent dosing for the cohort shall not commence until satisfactory review of these data is complete.

If at any time during cohort enrollment data suggest that stopping rules may have been met then dosing will be suspended. A formal review of available data by the Sponsor study team will determine whether stopping rule criteria have been met.

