### 5.2. Subject Compliance

Subjects assigned to SC cohorts will receive weekly treatment administration Day 1 to Day 78 (see [Section 3.2](#)). Subjects assigned to the IV cohort will receive monthly treatment administration from Day 1 to Day 57.

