### 9.3. Analysis of Pharmacokinetic Endpoints

For non-compartmental analysis (NCA) calculations with QW dosing frequency, the Day 36 plasma concentration will be imputed as the same as the Day 29 concentration.

The concentration of PF-06741086 will be descriptively summarized by PK dose and study day. Individual subject and median profiles of the PF-06741086 concentration versus time data will be plotted by dose using actual and nominal times respectively. Median profiles will be presented on both linear and logarithmic scales.

Noncompartmental PK parameters for PF-06741086 will be descriptively summarized by dose level and study day in accordance with Pfizer data standards.

Dose normalized  $AUC_{\tau}$  and  $C_{max}$  of PF-06741086 will be plotted against dose (using a logarithmic scale), and will include individual subject values and the geometric means for each dose. These plots will be used to help understand the relationship between the PK parameters and dose.

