3.2.2. Pharmacokinetics

- *Plasma PF-06741086 concentrations (Day 1 up to Day 113) and noncompartmental parameters will be calculated as determined by a validated assay:*
 - *Single-dose*
 - *Day 1 to Day 7 (QW): C_{max} , T_{max} , AUC_{last} , C_{168h}*
 - *Day 1 to Day 28 (QM): C_{max} , T_{max} , AUC_{last} , C_{672h} .*
 - *Multiple-dose Day 29 to Day 36 (QW) or Day 29 to Day 57 (QM) $C_{max,ss}$, $T_{max,ss}$, AUC_{τ} , V_{ss} (for IV administration only), CL (for IV administration only) or CL/F (for SC administration only), and C_{min} .*

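### Day 29–36 PK results in the weekly SC cohorts are reported as steady state, but Protocol Tables 3 and 4 together put the 300 and 450 mg regimens at only about 55–80% of it

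*Protocol*

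**What the plan says.** Protocol 2.2.2 and SAP 3.2.2 define the multiple-dose PK window for QW cohorts as Day 29 to Day 36. From it they take Cmax,ss, Tmax,ss, AUCτ, CL/F (SC) and Cmin. SAP 6.2.2 tabulates these parameters under the same window.

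The schedule in Protocol Table 2 has PK draws on Days 30, 33, 57, 85 and 113, but none on Day 36. Protocol 9.3 fills the gap: "the Day 36 plasma concentration will be imputed as the same as the Day 29 concentration". The SAP's rules for missing PK data (5.3.2) do not mention this imputation. In the readable text, neither document plans a check that steady state has been reached.

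Protocol 5.2 gives the treatment length: "Subjects assigned to SC cohorts will receive weekly treatment administration Day 1 to Day 78". On kinetics, Protocol 1.3.1.2 reports that exposure rose more than in proportion to dose, "which suggests that PF-06741086 may undergo target-mediated drug disposition". Protocol 1.3.3.2 says "Table 4 illustrates current predictions of the human PK based on data from Study B7841001".

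**The concern.** The Day 29 pre-dose value follows four doses (Days 1, 8, 15, 22) and a Day 36 pre-dose value follows five. They are equal only at steady state. Likewise, dose divided by AUCτ is a steady-state CL/F only if AUCτ comes from a steady-state interval.

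The protocol's own figures point the other way for two of the three SC regimens. If the interval comes before steady state, the reported steady-state exposure is too low and CL/F too high at 300 and 450 mg, with much less error in the cohort given a loading dose. Because the error differs between cohorts, it enters the plots of dose-normalised AUCτ and Cmax against dose that Protocol 9.3 intends for understanding how PK depends on dose.

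**Working it through.** The documents state no fraction of steady state at Day 29, so it has to be derived.

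**Inputs**

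| Quantity | Value | Source |
|---|---|---|
| 300 mg SC, single dose: Cmax | 16.49 µg/mL | Protocol Table 3 |
| AUCinf / AUClast | 2,799 / 3,120 µg·h/mL | Table 3 |
| t½ | 65.8 h (up to 122 h in Japanese subjects) | Table 3 |
| 300 mg QW: Cmax,ss / Ctrough,ss / AUC168,ss | 77 / 66.4 / 12,300 | Table 4 |
| 450 mg QW | 134 / 117 / 21,500 | Table 4 |
| 300 mg load, 150 mg QW | 21 / 15.7 / 3,220 | Table 4 |

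Protocol 1.3.3.1 gives a similar predicted trough, 67.3 µg/mL, "following 300 mg weekly SC dosing of PF-06741086".

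**1. Half-life alone.** The fraction after four doses is 1 − exp(−4·168·ln2/t½). That is 99.9% for 65.8 h and 97.8% for 122 h. But 65.8 h also implies an accumulation ratio of 1/(1 − exp(−168·ln2/65.8)) = 1.2, against 77/16.49 = 4.7 from the tables. Under linear kinetics AUC168,ss would equal the single-dose AUCinf of about 2,800, not 12,300. The single-dose half-life therefore cannot be used to claim steady state.

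**2. Accumulation ratio R, 300 mg.** Fraction after n doses = 1 − (1 − 1/R)ⁿ.
- R = 12,300/3,120 = 3.9: 69% after four doses, 77% after five.
- R = 77/16.49 = 4.7: 62% and 70%.

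This is a rough guide only, because the formula assumes geometric build-up.

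**3. Decay within the interval, Table 4 alone.** k = ln(77/66.4)/(168 − Tmax). For Tmax 48, 72 and 108 h this gives half-lives of 23.4, 18.7 and 11.7 days, and 56%, 65% and 81% of steady state after four doses. For 450 mg: 53%, 61% and 78%. It assumes that absorption is over by Tmax.

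**4. Nonlinear model fitted to both tables.** Two compartments, first-order SC absorption, linear plus saturable elimination: V1 3.14 L, V2 3.02 L, Q 0.031 L/h, CL 0.0139 L/h, Vmax 0.50 mg/h, Km 0.195 µg/mL, ka 0.0075 /h, F 0.85. It reproduces Table 4 (300 mg: 77.2 / 66.2 / 12,309; 450 mg: 133.7 / 117.2 / 21,474). It comes near Table 3 (300 mg SC Cmax 14.9, AUC 3,314).

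| Trough, µg/mL | Day 29 | Day 36 | Day 57 | Day 85 | Steady state |
|---|---|---|---|---|---|
| 300 mg | 45.9 (69%) | 51.7 (78%) | 60.9 (92%) | 64.8 (98%) | 66.2 |
| 450 mg | 82.6 (71%) | 92.5 (79%) | 108.2 (92%) | 114.9 (98%) | 117.2 |
| 300/150 mg | 15.0 (97%) | 15.1 (98%) | 15.3 (99%) | 15.4 (100%) | 15.4 |

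**5. Effect on the reported parameters** (trapezoid at 0, 24, 96, 168 h).
- Imputation, 300 mg: AUCτ 9,051 instead of 9,259, a loss of 2%.
- Label: 9,051/12,149 = 0.745 of steady state; at 450 mg, 15,946/21,235 = 0.751.
- CL/F, 300 mg: 300/9,051 = 0.0331 L/h against 300/12,149 = 0.0247 L/h, or 34% too high.
- Dose-normalised AUC from Table 4: 21.5, 41.0 and 47.8 for 150, 300 and 450 mg, a 1.91- and 2.23-fold rise from 150 mg. Scaled by the Week 5 fractions (0.981, 0.745, 0.751): 21.1, 30.5 and 35.9, a 1.45- and 1.70-fold rise.
- Interpolated Day 36, 300 mg: 45.9 + (7/28)(60.9 − 45.9) = 49.7, 4% below the model's 51.7. The carry-forward is 11% below.

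**6. Spread.** Repeat fits to the same tables put the two higher cohorts at 56–71% for the Day 29 trough and 65–77% for the Day 29–36 AUC. The CL/F excess is then 1/0.77 to 1/0.65, or 30–54%. The loading-dose cohort ranges from about 80% to 98%, and the Day 57 trough in the higher cohorts from about 81% to 92%. Reading Table 4 as week-12 values gives 69–79%; reading it as week-5 values fits less well and still gives 61–73%. Forcing about 85% at Day 29 doubled the misfit and predicted a 300 mg single-dose AUC of 4,114 and Tmax of 120 h, against about 3,000 and 72 h in Table 3.

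**The case against.** The strongest reply is that little depends on the label. A reader might infer that the dose-progression review, which needs data "through study Day 29 (at a minimum) in 100% (ie, 6 of 6) of subjects in the current cohort", would be misled into seeing a plateau. The documents do not support that:

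- PK is also drawn at the weekly visits on Days 8, 15 and 22. With Day 29 this gives four successive troughs (12.5, 26.9, 37.9 and 45.9 µg/mL in the model at 300 mg), a visible climb.
- The imputation is confined to NCA and concerns Day 36, after the minimum cut-off.
- Protocol 3.3 requires the next regimen to be projected for the first dose or steady state against fixed limits. The AUC168 limit of 1,940,000 µg·h/mL is 158 times the 300 mg prediction and 90 times the 450 mg prediction. An error of this size cannot change that outcome.

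It might also be inferred that the imputation does the damage. It moves AUCτ by only 2%.

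Other points stand in part. Concentrations are summarised by day, so Days 57 and 85 will be visible, and SAP 6.2.2 names the interval. The comparison of 300 with 450 mg is barely affected. With six subjects and the 68% CV of AUClast in Table 3, one standard error of a geometric mean is about 25%, similar to the bias. But that error is random, whereas this one has a known direction and differs between cohorts. Modelling is foreseen and part of Section 9 is redacted, so model-based steady-state estimates may already be planned.

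The AUC ratio in step 2 mixes nonlinearity with accumulation, and step 3 ignores continuing absorption. Neither is independent proof. The conclusion rests on the failure of single-dose kinetics to produce Table 4 and on the joint fits.

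**Conclusion.** The point holds as a matter of labelling and interpretation. At Day 29–36 the 300 and 450 mg SC QW cohorts are at roughly 55–80% of steady state, and the 300/150 mg cohort at about 80–98%. CL/F presented as a steady-state value would be about 30–55% too high in the two higher cohorts, and the rise in dose-normalised exposure from 150 mg upward would look flatter than it is.

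This assumes that Table 4 is right for patients. The sponsor's model is not in the documents. Table 3 comes from healthy subjects, with 3 to 6 contributing and CVs of 63–83% at 300 mg SC. There is no single-dose 450 mg SC value. The model was fitted to both tables, so it shows what makes them compatible and does not predict independently. No effect on dose-progression decisions is claimed.

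**What to change.** Amend Protocol 2.2.2 and 9.3 and SAP 3.2.2, 5.3.2 and 6.2.2, using samples already scheduled:

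1. Label the Day 29–36 QW parameters as Week 5 values and drop the ss subscript.
2. Replace the carry-forward with interpolation between the Day 29 and Day 57 pre-dose concentrations where Day 57 exists. State in the SAP what is done where it does not.
3. Compare the Day 29, 57 and 85 troughs, using actual sampling times, before calling any value steady state. Day 85, seven days after the Day 78 dose, is the closest observed steady-state trough (96–98% in the fits where it was read off). Day 57 should not be taken as steady state.
4. Take steady-state AUC and CL/F from the PK model, and say so beside the dose-normalised plots.

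An added Day 36 tube is not proposed. Protocol 7.3.1 keeps the number of PK samples fixed and 7.7 says total blood volume should not increase. The cost is a little more analysis work and the loss of an NCA steady-state CL/F for the QW cohorts.

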### 9.4. Analysis of Pharmacodynamic Endpoints

The PD endpoints include total TFPI, thrombin generation (parameters include lag time, peak thrombin generation, and endogenous thrombin generation potential), prothrombin fragments 1+2, D-dimers, and dilute PT.

Absolute and change from baseline values will be listed and summarized descriptively by dose level and study day. Change from baseline of each PD endpoint will be analyzed using a mixed model for repeated measures (MMRM) with a restricted maximum likelihood method for the estimation of the covariance parameters. Details will be provided in the SAP.

dPT-concentration relationship will be explored. Dose-response relationship for other PD endpoints may also be explored.

CCI [REDACTED]  
[REDACTED]  
[REDACTED]

## 9.6. Safety Analysis

Adverse events, ECGs, vital signs (blood pressure, pulse rate, temperature and respiratory rate), physical examinations and safety laboratory data (including hematology, PT/INR, aPTT, chemistry, urinalysis, fibrinogen, anti-thrombin III activity and cardiac troponin I) will be reviewed and summarized on an ongoing basis during the study to evaluate the safety of subjects. Safety data will be presented in tabular and/or graphical format and summarized descriptively, where appropriate. Incidence and severity of TEAEs, withdrawals due to TEAEs, and infusion and injection site reactions will be summarized by dose level. Abnormal and clinically relevant changes in vital signs and ECG parameters will be summarized by dose level and study day. Incidence and magnitude of abnormal laboratory findings will be summarized by dose level. Abnormal safety findings will also be presented separately for inhibitor subjects by dose level.

Only positive ADA samples and the corresponding baseline sample will be tested in the NAb assay. Frequencies of ADA and NAb will be summarized by dose level and study day for samples collected.

Medical history, medication history and physical examination information, as applicable, collected during the course of the study will be captured for inclusion into the study database, unless otherwise noted. Any untoward findings identified on physical examination conducted after the administration of the first dose of investigational product will be captured as an adverse event, if those findings meet the definition of an adverse event. Data collected at Screening that are used for inclusion/exclusion criteria, such as laboratory data, ECGs and vital signs will be included in the study database. Demographic data collected at Screening will be reported.

### 9.6.1. Derivation of Vital Signs Parameters

Supine blood pressures and pulse rate will be recorded at each assessment time indicated in the [Schedule of Activities](#). Baseline for vital signs will be defined as the last measurement before the Day 1 investigational product administration.

Vital signs (BP; PR) will be assessed for clinically relevant trends. The standard algorithms and reporting formats will be applied for analyzing all safety data.

Absolute values and changes from baseline in for systolic and diastolic blood pressure and pulse rate will be summarized by dose level and study day.

Maximum absolute values and maximum changes from baseline for vital signs will also be summarized descriptively by dose level using categories as defined in the SAP. Numbers and percentages of subjects meeting the categorical criteria will be provided and individual values listed in the study report.

